#### INSTRUCTIONS

This template is intended to help investigators prepare a protocol that includes all of the necessary information needed by the IRB to determine whether a study meets approval criteria. **Read the following instructions before proceeding:**

1. Use this protocol template for a PI initiated study that includes direct interactions with research subjects. Additional templates for other types of research protocols are available in the system Library.
2. If a section or question does not apply to your research study, type "Not Applicable" underneath.
3. Once completed, upload your protocol in the "Basic Information" screen in IRES IRB system.

## SECTION I: RESEARCH PLAN

1. **Statement of Purpose:** State the scientific aim(s) of the study, or the hypotheses to be tested.

The specific aims of Sub-study #1 are:

Specific Aim #1: DEVELOPMENT: We will update our current Invite Only VR prototype into a polished videogame intervention using input from 4 focus groups of 5 adolescents each (n = 20), aged 12-17 and the extant literature. These focus groups will inform the development of the VR videogame intervention, *Invite Only VR*, for e-cigarette prevention among teens.

Specific Aim #2: EVALUATION: Conduct a pilot randomized controlled trial with 300 teens ages 11-15 comparing the Invite Only VR intervention vs. an attention/control non-health-related VR videogame, collecting assessment data at baseline, post-gameplay, three months and six months to determine:

- a. the preliminary impact of the intervention on knowledge, intentions, perceptions, attitudes, social norms, self-efficacy and behaviors related to: i) initiation of e-cigarette use, ii) e-cigarette use cessation.
- b. the intervention's acceptability and feasibility by collecting quantitative and qualitative data on teens' satisfaction and gameplay experience of the intervention.
- c. preliminary evidence of the impact of *Invite Only VR* on players' perception and experience of social pressure and social norm development.

The specific aim for Sub-study #2 is

Specific Aim #1: EVALUATION: Conduct a quasi-experimental effectiveness trial of the Invite Only VR intervention using a pre-post study design with 400 teens ages 11-15, collecting assessment data at baseline and post-gameplay to determine:

- a. the preliminary impact of the intervention on knowledge, intentions, perceptions, attitudes, social norms, self-efficacy and behaviors related to: i) initiation of e-cigarette use, ii) e-cigarette use cessation.
- b. the intervention's acceptability and feasibility by collecting quantitative on teens' satisfaction and gameplay experience of the intervention.

2. **Probable Duration of Project:** State the expected duration of the project, including all follow-up and data analysis activities.

2 years

3. **Background:** Describe the background information that led to the plan for this project. Provide references to support the expectation of obtaining useful scientific data.

Tobacco use, including the use of e-cigarettes, is the leading cause of preventable disease and death in the United States and is linked to cancer and cardiovascular diseases. In 2016, 3.9 million middle/high school students used at least one tobacco product in the past 30 days and approximately 45% of middle/high school students used two or more tobacco products in the past 30 days. Of particular interest, e-cigarettes have emerged as an introductory tobacco product among youth due, in part, to their appealing flavors and perception that they are safer than other products. Given more than 80% of adult smokers begin using tobacco products such as e-cigarettes before the age of 18, there is a

need to develop interventions that will help prevent e-cigarette experimentation among young adolescents; a population inherently vulnerable to tobacco initiation and the development of life-long tobacco use.

The use of virtual reality (VR) has emerged as an effective intervention approach to addressing a range of health issues, including phobias, social anxiety, post-traumatic stress disorder and pain management. Currently, no research exists on the efficacy of evidence-based VR videogames related to tobacco use prevention.

4. **Research Plan:** Summarize the study design and research procedures using non-technical language that can be readily understood by someone outside the discipline. **Be sure to distinguish between standard of care vs. research procedures when applicable, and include any flowcharts of visits specifying their individual times and lengths.** Describe the setting in which the research will take place.

The goal of this research study is to conduct a randomized controlled trial of the VR-based e-cigarette prevention intervention, *Invite Only VR*, with the aim to prevent the initiation of e-cigarette use in teens by increasing their knowledge, decreasing their intentions to use e-cigarettes, influencing their harm perceptions and attitudes associated with e-cigarettes, and increasing behavioral skills associated with refusing peers involving e-cigarettes. *Invite Only VR* is an innovative, immersive intervention that may hold the promise to reducing e-cigarette initiation in teens.

For Sub-study #1:

We will conduct the proposed research for the study in two phases. Phase I consists of: (a) the continued development of our current *Invite Only VR* prototype into a polished videogame intervention using input from 4 focus groups of 5 adolescents each (n = 20), aged 12-17 and the extant literature. These focus groups will inform the development of the VR videogame intervention, *Invite Only VR*, for e-cigarette prevention among teens (Specific Aim #1). In Phase II, we will conduct a randomized controlled trial with 300 teens ages 11-15 comparing the *Invite Only VR* intervention vs. an attention/control non-health-related VR videogame, collecting assessment data at baseline, post-gameplay, three months and six months to determine: 1) the preliminary impact of the intervention on knowledge, intentions, perceptions, attitudes, social norms, self-efficacy and behaviors related to initiation of e-cigarette use and e-cigarette use cessation, 2) the intervention's acceptability and feasibility by collecting quantitative and qualitative data on teens' satisfaction and gameplay experience of the intervention, and 3) preliminary evidence of the impact of *Invite Only VR* on players' perception and experience of social pressure and social norm development.

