**Conduct focus groups to gather data to inform refinement of the current videogame prototype, *Invite Only VR*.**

We will conduct 4 focus groups (5 adolescents each) to collect feedback on the game content, art, narrative, and characters, and gameplay mechanics. We will use visual tools (e.g., storyboards, pictures) to facilitate the discussions. We will conduct the focus groups according to standard dual-facilitator procedures. We anticipate that 4 focus groups will be adequate to achieve thematic saturation. The focus groups will be conducted such that ideas and themes from one discussion inform discussion topics and prompts used in the next focus group. Participants will be compensated with a gift card for \$25. Audio recordings of each session will be transcribed, reviewed and discussed by the research team to refine the videogame intervention. As a part of the game development, with parental permission we will invite selected students to the Yale recording studio on campus to provide voices for the videogame characters.

**Conduct randomized controlled trial:** We will enroll 300 adolescents to test *Invite Only VR* using a pre/post design to evaluate the preliminary efficacy of the videogame prototype, *Invite Only VR*. Participants will be randomly assigned to play either Invite Only VR (n=115), or receive standard care as usual (n=115). Participants will accumulate between 1.5-2 hours of game play over 2 sessions (approximately one week, meeting twice). Participants will play the *Invite Only VR* game on a VR headset for 45 mins to 1 hour, one to two times per week for 2 weeks (to accumulate up to 1.5 - 2 hours of gameplay). This total duration and number of sessions is consistent with those found in effective smoking prevention interventions among adolescents and with the amount of time adolescents play videogames. Participants will have a 10 min break in the middle of each session and will be instructed that they may take additional breaks as needed.

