|  Decisionally Impaired |  Employees                         |  Pregnant women and/or fetuses           |
|  Yale Students         |  Females of childbearing potential |                                                                  |

NOTE: Is this research proposal designed to enroll children who are wards of the state as potential subjects?

Yes  No

8. **Inclusion/Exclusion Criteria:** What are the criteria used to determine subject inclusion or exclusion?

For the focus groups and pilot-testing, inclusion/exclusion criteria are: participants must be 12-17 years of age and speak English. For the randomized controlled trial, participants must be between the ages of 11-15, Speak English, and be able to play a mobile app-based videogame and VR videogame (willing to sit with a smartphone or tablet computer and/or use a VR headset for 45-60 minutes/session to play the game). Eligibility will be determined by the research team.

9. How will **eligibility** be determined, and by whom?

Eligibility will be determined by the research team. If a prospective participant meets the inclusion criteria, they will be eligible to participate in the project.

10. **Risks:** Describe the reasonably foreseeable risks, including risks to subject privacy, discomforts, or inconveniences associated with subjects participating in the research.

The potential risks associated with this study have to do with maintenance of the confidentiality of the identities of the participants enrolled in the study and information relating to them. De-identified hard copies of the data will be stored in locked cabinets and electronic data will be stored in secure, password-protected computers. Only the P.I. and other relevant research staff will have access to the data.

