Statistical procedures and models for analyzing data have been selected according to the research hypotheses being investigated and the types of data available. In general, we will use two-tailed tests and p-values smaller than 0.05 will be considered to indicate statistical significance. When necessary, however, we will use appropriate adjustment of the level of significance (alpha) to account for multiple statistical tests. All statistical analyses will be conducted on an intention-to-treat sample using either SPSS/SAS statistical packages. Baseline characteristics will be analyzed using descriptive statistics.

We will evaluate the efficacy of Invite Only VR at reducing initiation of e-cigarette use (primary outcome). We will test the hypothesis that individuals who play Invite Only VR will be less likely to report the initiation of e-cigarette use in comparison to the control condition. We will conduct a longitudinal analysis using a linear mixed models approach to compare participants in the intervention group to participants in the control group on e-cigarette use from baseline across all follow-up assessments. An advantage of mixed models is that participants with missing data need not be excluded as all available data are used in estimating parameters. We will also use logistic regression models to determine if any relevant baseline variables are associated with rates of initiation of e-cigarette use (constructed as a binary outcome (Yes/No). We plan to evaluate the prognostic significance of a small set of predictor variables (e.g., knowledge, intentions, perceptions, attitudes, social norms, and self efficacy) and use them as covariates in the primary analysis.

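### The pilot RCT lists cessation of e-cigarette use as an impact outcome, but its unselected 11-15 school sample and its analysis plan cannot give an informative cessation comparison

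*Combined protocol and SAP*

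**What the plan says.** Section I, item 1 (Statement of Purpose), Aim 2 of Sub-study #1 reads "Conduct a pilot randomized controlled trial with 300 teens ages 11-15". Part (a) of that aim covers "behaviors related to: i) initiation of e-cigarette use, ii) e-cigarette use cessation". Item 4 (Research Plan), Phase II, repeats both outcomes: "self-efficacy and behaviors related to initiation of e-cigarette use and e-cigarette use cessation". The impact is described as preliminary, and the comparison is between the VR game and a control condition.

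The rest of the plan concerns prevention:

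- **Intervention.** Item 4 describes the game as an intervention "with the aim to prevent the initiation of e-cigarette use in teens".
- **Population.** Item 8 gives the RCT criteria: "participants must be between the ages of 11-15, Speak English, and be able to play a mobile app-based videogame and VR videogame". E-cigarette use is neither required nor excluded. Under Study locations in item 4, RCT enrolment is from one middle-school district, most of whose students are 11 to 14.
- **Measures.** Item 4 lists intentions to start, refusal self-efficacy, norms, attitudes and smoking behaviour, at baseline, after gameplay, and at 3 and 6 months. None is specific to quitting, and cessation is not defined.
- **Analysis.** Item 13 (Statistical Considerations) says "We will evaluate the efficacy of Invite Only VR at reducing initiation of e-cigarette use (primary outcome"), states one hypothesis, on initiation, and compares the arms on e-cigarette use over time in an intention-to-treat sample. It contains no cessation hypothesis, user subset or cessation comparison.

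**The concern.** Cessation can be observed only in people who use e-cigarettes, which in this trial means mainly those already using at baseline. The plan neither recruits such people nor says how many it expects, and it does not say how stopping would be defined or compared. The aim therefore has no selected population, no endpoint and no analysis behind it.

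Any cessation result would have to be constructed after the fact from a small subset balanced only by chance. Because cessation is a stated aim, such a result could still be presented as a pre-specified finding, in either direction.

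A linked problem affects the primary outcome. Item 13 does not say that baseline users are left out of the initiation analysis, although they cannot initiate. Mixing them in with those at risk means that the model of use over time does not separate not starting from stopping.

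**Working it through.** **1. The plan's own figure.** The RCT size is 300 (items 1 and 4; Section III, item 1). No power, effect size, event rate or dropout is given, so 300 cannot be reproduced. The arms stated in item 4 sum to 115 + 115 = 230, not 300. That mismatch is a separate matter; both totals are carried here.

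**2. Baseline use rate.** None is given. The Background offers only a national count of middle and high school students using any tobacco product, without a denominator. I assume 1% to 20%.

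**3. Expected users and precision.** Users = N × rate, split equally between arms. The approximate 95% half-width for the difference in the proportion stopping is 1.96 × √(2 × p × (1 − p) / n), with n users per arm and p = 0.4 assumed in both arms. No dropout is assumed.

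| Assumed use rate | Users of 300 | Users of 230 | Half-width, N = 300 | Half-width, N = 230 |
|---|---|---|---|---|
| 1% | 3 | 2 | over 100 points (no usable interval) | over 100 points |
| 3% | 9 | 7 | ±64 | ±73 |
| 5% | 15 | 12 | ±50 | ±57 |
| 10% | 30 | 23 | ±35 | ±40 |
| 15% | 45 | 35 | ±29 | ±33 |
| 20% | 60 | 46 | ±25 | ±28 |

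Worked example at 20% of 300: n = 30 per arm, 1.96 × √(0.48 / 30) = 1.96 × 0.126 = 0.25.

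The normal approximation is poor for a few users per arm, so the top rows only show scale.

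**4. Sensitivity to the assumed quit proportion.** At n = 30 per arm and p = 0.2, the half-width is 1.96 × √(0.32 / 30) = 0.20. That is narrower in points, but as large as the quit proportion itself.

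**5. Power, for reference only, since none is promised.** Two-sided 0.05, normal approximation, without continuity correction:

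- At 20% use (30 per arm), power is 39% for quit rates of 20% vs 40%, and 65% for 30% vs 60%.
- At 10% use (15 per arm), it is 22% and 37%. Fisher's exact test gives 11% and 23%.
- For 80% power, 20% vs 40% needs 82 per arm, 164 users in all: 164 / 300 = 55% of those enrolled. For 30% vs 60% it needs 42 per arm, 84 users: 84 / 300 = 28%.

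**6. Effect of the fix on the initiation set.** Removing baseline users leaves 300 − 60 = 240 to 300 − 3 = 297 participants, or 230 − 46 = 184 to 230 − 2 = 228.

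**The case against.** The strongest reply is that this is a pilot, that the aim is worded as preliminary impact, and that no power for cessation is promised. That stands: low power alone is no fault here, and the point rests on precision and on the missing definition and analysis.

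Four further replies have some force:

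- **A reader might infer that the trial will report a misleading effect on cessation.** The documents do not support that. Item 13 plans no cessation test. The defect is an aim without a matching analysis, which leaves room for an ad hoc one.
- **A reader might infer that only a handful of participants could contribute.** That depends on a use rate the documents do not give. At 1-5% the number is about 2 to 15; at 20% it is 46 to 60.
- **Cessation is not strictly confined to baseline users.** Someone who starts by month 3 and stops by month 6 would also show it. The aim also names knowledge and attitudes, which could be asked of non-users. Neither supplies a defined between-arm cessation comparison.
- **Smoking behaviour is measured at all four times, and the mixed model covers use.** So stopping enters the data and the model, though not separately from starting. This supports a descriptive table; it does not provide an estimate of effect on cessation.

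**Conclusion.** The point holds in a limited form. The RCT lists cessation as an outcome on which it will determine preliminary between-arm impact, yet it selects no users, tests a prevention game, and has no definition or comparison for cessation. Those facts are in the documents and do not depend on any assumed rate.

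The size does depend on assumptions: 1-20% baseline use, equal arms, no dropout and about 40% stopping. On these there would be about 3-60 users of 300 (2-46 of 230), and the interval for a difference in quitting would be about ±25 points at best and much wider at lower use rates. Dropout would widen it further.

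It would go too far to say that the objective cannot be addressed at all: the trial can describe what baseline users do. What it cannot give is an informative comparison of arms. Initiation remains the primary outcome, but the plan should say who is at risk of it.

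**What to change.** **Section I, items 1 and 4 (Sub-study #1, RCT).** Remove cessation from the outcomes on which impact is determined. Label it exploratory and descriptive: counts of e-cigarette use at 3 and 6 months, by arm, among participants who report use at baseline, with no test and no impact claim. State how baseline use is defined.

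**Section I, item 13.** State, as an explicit change to the analysis set, that initiation is evaluated among randomised participants who report no e-cigarette use at baseline, analysed as randomised, because baseline users cannot initiate. The current text has no such restriction, so it should not be presented as a clarification.

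**Cost.** Revised wording and one table from data already planned, with no extra enrolment or assessments. The sponsor gives up a cessation claim that the design cannot support, and the initiation set shrinks by the share of baseline users (1-20% under the assumption above).

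Sub-study #2 uses the same cessation wording in a single-arm design that ends after gameplay. It needs separate consideration and is not covered by this change.

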**Conduct focus groups to gather data to inform refinement of the current videogame prototype, *Invite Only VR*.**

We will conduct 4 focus groups (5 adolescents each) to collect feedback on the game content, art, narrative, and characters, and gameplay mechanics. We will use visual tools (e.g., storyboards, pictures) to facilitate the discussions. We will conduct the focus groups according to standard dual-facilitator procedures. We anticipate that 4 focus groups will be adequate to achieve thematic saturation. The focus groups will be conducted such that ideas and themes from one discussion inform discussion topics and prompts used in the next focus group. Participants will be compensated with a gift card for \$25. Audio recordings of each session will be transcribed, reviewed and discussed by the research team to refine the videogame intervention. As a part of the game development, with parental permission we will invite selected students to the Yale recording studio on campus to provide voices for the videogame characters.

**Conduct randomized controlled trial:** We will enroll 300 adolescents to test *Invite Only VR* using a pre/post design to evaluate the preliminary efficacy of the videogame prototype, *Invite Only VR*. Participants will be randomly assigned to play either Invite Only VR (n=115), or receive standard care as usual (n=115). Participants will accumulate between 1.5-2 hours of game play over 2 sessions (approximately one week, meeting twice). Participants will play the *Invite Only VR* game on a VR headset for 45 mins to 1 hour, one to two times per week for 2 weeks (to accumulate up to 1.5 - 2 hours of gameplay). This total duration and number of sessions is consistent with those found in effective smoking prevention interventions among adolescents and with the amount of time adolescents play videogames. Participants will have a 10 min break in the middle of each session and will be instructed that they may take additional breaks as needed.

**Measures.** We will collect data on participant demographics at baseline. At baseline and immediately after gameplay, and again at 3 and 6 months post gameplay, we will collect data on intentions to initiate smoking, self-efficacy for refusing offers of e-cigarettes and other tobacco products, perceived social norms related to smoking, attitudes about smoking, and smoking behavior using validated questionnaires. Finally, we will assess satisfaction with game play and acceptability and feasibility of the intervention by collecting self-report data at the end of the game play period. All assessments will be conducted via face-to-face interviews with a research assistant and each adolescent.

**Study locations.** For the focus groups and pilot-testing, the study will take place at one of the after-school programs with which the play2PREVENT Lab has ongoing partnerships including but not limited to: Wilbur Cross High School (which serves 1300 students from 9th to 12th grade), Hamden Youth Center (which serves roughly 75 adolescents in the 6th through 12th grade, and the Milford Middle School District (which serves 1300 students the majority of whom are between the ages of 11 and 14), and LEAP (which serves over 1000 children between the ages of 7-18). For the randomized controlled trial, we will enroll students from the Milford Middle School District between the ages of 11-15.

**Participants, screening, and consent.** In collaboration with community program staff, we will discuss the study with interested parents and adolescents and collect eligibility screening data. If the participant is eligible and interested we will proceed with the consent procedures that will differ by phase of the research. For focus groups, we will give information sheets to the adolescents and to their parents describing the purpose of and protocol for the focus groups. Parents who do not wish for their children to participate will contact the project director. No forms will be signed for focus groups. For the randomized controlled trial, we will obtain written, informed assent (adolescent) and consent (parent).

In addition to paper forms for parental consent for participation in the randomized controlled study, we will also provide a web-based form for parents to review and electronically sign through Yale Qualtrics.

For Sub-study #2:

We will conduct a quasi-experimental study with 400 teens from the Seattle School District ages 11-15 of the *Invite Only VR* intervention collecting assessment data at baseline and post-gameplay to determine: 1) the preliminary impact of the intervention on knowledge, intentions, perceptions, attitudes, social norms, self-efficacy and behaviors related to initiation of e-cigarette use and e-cigarette use cessation, and 2) the intervention's acceptability and feasibility by collecting quantitative on teens' satisfaction and gameplay experience of the intervention.

**Quasi-experimental study design:** With the assistance of our program partners at Seattle Schools, we will enroll 400 adolescents to test *Invite Only VR* using a pre/post design to evaluate the preliminary efficacy of the videogame prototype. All participants will play Invite Only VR. Participants will accumulate between 1.5-2 hours of game play during their class or program time. Participants will play the *Invite Only VR* game on a VR headset for 45 mins to 1 hour, one to two times (to accumulate up to 1.5 - 2 hours of gameplay) during their advisory/common time in school (non-class time). This total duration and number of sessions is consistent with those found in effective smoking prevention interventions among adolescents and with the amount of time adolescents play videogames. Program partners will be instructed to give participants a 10 min break in the middle of each session and will be instructed that they may take additional breaks as needed.

**Measures.** We will collect data on participant demographics at baseline. At baseline and immediately after gameplay, we will collect data on intentions to initiate smoking, self-efficacy for refusing offers of e-cigarettes and other tobacco products, perceived social norms related to smoking, attitudes about smoking, and smoking behavior using validated questions adapted from the Youth Risk Behavior Survey (Kann et al, 2018.) Finally, we will assess satisfaction with game play and acceptability and feasibility of the intervention by collecting self-report data at the end of the game play period. All assessments will be conducted on a secured Qualtrics website with instructions from school program staff.

**Study locations.** Students will be enrolled from within the Seattle School District in Seattle, Washington. School program staff will select classes and teachers to participate in the study with an option to opt-out.

**Participants, screening, and consent.** In collaboration with community program staff at Seattle School District, an information letter describing the study will be provided to interested parents and adolescents. Letters will be sent home with each child and an announcement about the letter will be emailed to parents. If the participant is eligible and interested, they will be enrolled in the study. If a parent or participant does not want to participate in the study, they may choose to opt out by contacting the school program staff. [name] will call in through a live video-feed call through Zoom and provide a face-to face conversation with teens from classes that have been chosen by the school to participate in the study to describe the study and provide time for questions. Teens will also be provided [name] phone number to call with any additional questions or clarification.

5. **Genetic Testing**      N/A

6. **Subject Population:** Provide a detailed description of the types of human subjects who will be recruited into this study.

Adolescents ages 11-17 will be recruited into this study.

7. **Subject classification:** Check off all classifications of subjects that will be specifically recruited for enrollment in the research project. Will subjects who may require additional safeguards or other considerations be enrolled in the study? If so, identify the population of subjects requiring special safeguards and provide a justification for their involvement.

- |                                                |                                                            |                                                                  |
|------------------------------------------------|------------------------------------------------------------|------------------------------------------------------------------|
|  Children   |  Healthy                |  Fetal material, placenta, or dead fetus |
|  Non-English Speaking  |  Prisoners                         |  Economically disadvantaged persons      |
|  Decisionally Impaired |  Employees                         |  Pregnant women and/or fetuses           |
|  Yale Students         |  Females of childbearing potential |                                                                  |

NOTE: Is this research proposal designed to enroll children who are wards of the state as potential subjects?

Yes  No

8. **Inclusion/Exclusion Criteria:** What are the criteria used to determine subject inclusion or exclusion?

For the focus groups and pilot-testing, inclusion/exclusion criteria are: participants must be 12-17 years of age and speak English. For the randomized controlled trial, participants must be between the ages of 11-15, Speak English, and be able to play a mobile app-based videogame and VR videogame (willing to sit with a smartphone or tablet computer and/or use a VR headset for 45-60 minutes/session to play the game). Eligibility will be determined by the research team.

9. How will **eligibility** be determined, and by whom?

Eligibility will be determined by the research team. If a prospective participant meets the inclusion criteria, they will be eligible to participate in the project.

10. **Risks:** Describe the reasonably foreseeable risks, including risks to subject privacy, discomforts, or inconveniences associated with subjects participating in the research.

The potential risks associated with this study have to do with maintenance of the confidentiality of the identities of the participants enrolled in the study and information relating to them. De-identified hard copies of the data will be stored in locked cabinets and electronic data will be stored in secure, password-protected computers. Only the P.I. and other relevant research staff will have access to the data.

Playing *Invite Only VR* may pose a potential psychological risk in that we address sensitive issues around tobacco use and its consequences. Research staff will be available to provide assistance to the participants, answer their questions, and serve as a resource if any distress or concern arises. The assessments and instruments may also present a potential risk given that some of the questions are sensitive in nature and address issues around substance use. Again, the Research staff will be available to assist the participants, the program sites staff, and the research staff members administering the assessments if there appears to be any distress around the questions being asked. If participants need additional or more intensive attention, [name] will provide consultation to the participant.

Also the use of a virtual reality headset for the project may pose a slight physical risks for the participants in the form of dizziness, queasiness, seizures (about 1 in 4000 experience this effect), eye or muscle twitching, and faintness.

11. **Minimizing Risks:** Describe the manner in which the above-mentioned risks will be minimized.

A number of precautions will be actively integrated into the research procedures to protect the confidentiality and anonymity of all participants. All research staff and the staff and volunteers participating in the intervention will be required to complete training in research ethics. Data collection forms will be designated by ID numbers only. A separate master file of names, addresses, contact persons, and telephone numbers, along with the study ID numbers will be maintained in a locked file cabinet in the P.I.'s research offices. All data entry and analyses will be completed with ID numbers only. The study will be explained to others, such as the guardian/parent and program staff as a study of child development that will focus on promoting healthy behaviors. In instances in which data are requested from other sources or it is beneficial to the participant to provide information to another individual or agency (e.g. medical personnel) this will only be done with the written permission of the guardian/parent on a "Release of Information" form stipulating

who the information is provided to, or received from. The research staff will follow standard confidentiality procedures for research programs.

To minimize possible physical risks associated with the project, per the health and safety manual for the virtual reality headsets, participants will not be allowed to use the virtual reality headsets while they are tired, sleep impaired, if they have digestive problems, are under emotional stress or anxiety or suffering from a cold, flu, headache, migraine or earache. Additionally, participants using the virtual reality headsets will be required to take a 10-15 min break for every 30 mins of game play.

Furthermore, throughout their gameplay experience, to help minimize risk participants utilizing the VR headsets will be asked about how they are physically feeling. If the participant's answer indicates that they are experiencing any of the adverse physical symptoms, the research staff will immediately stop gameplay.

In the unlikely event that a participant involved with the study experiences a serious medical or psychological complication, that requires further attention, this would be reported to [name] who will then determine if further consultation is required without divulging the name of the individual, if this appeared appropriate and necessary. [name] would then be responsible for ensuring that the needs of the individual were addressed.

12. **Data and Safety Monitoring Plan:** Include an appropriate Data and Safety Monitoring Plan (DSMP) based on the investigator's risk assessment stated below. (Note: the HIC will make the final determination of the risk to subjects.)
- a. What is the investigator's assessment of the overall risk level for subjects participating in this study? Minimal risk
  - b. If children are involved, what is the investigator's assessment of the overall risk level for the children participating in this study? Minimal risk
  - c. Include an appropriate Data and Safety Monitoring Plan. Examples of DSMPs are available here <http://your.yale.edu/policies-procedures/forms/420-fr-01-data-and-safety-monitoring-plans-templates> for
    - i. Minimal risk
    - ii. Greater than minimal

The principal investigator is responsible for monitoring the data, assuring protocol compliance, and conducting the safety reviews quarterly. During the review process, the principal investigator will evaluate whether the study should continue unchanged, require modification/amendment, or close to enrollment.

The principal investigator or the Human Investigative Committee (HIC) have the authority to stop or suspend the study or require modifications.

This protocol presents minimal risks to the subjects and Unanticipated Problems Involving Risks to Subjects or Others (UPIRSOs), including adverse events, are not anticipated. In the unlikely event that such events occur, Reportable Adverse Events (which are events that are serious or life-threatening and unanticipated (or anticipated but occurring with a greater frequency than expected) and possibly, probably, or definitely related) or Unanticipated Problems Involving Risks to Subjects or Others that may require a temporary or permanent interruption of study activities will be reported immediately (if possible), followed by a written report within 5 calendar days of the Principal Investigator becoming aware of the event to the IRB via the RNI submission process in IRES IRB and any appropriate funding and regulatory agencies. The investigator will apprise fellow investigators and study personnel of all adverse events that occur during the conduct of this research project through regular study meetings and via email as they are reviewed by the principal

investigator. We will use procedures to detect and respond to adverse events that ensure prompt discovery of any adverse events and to minimize their effects. There is adequate surveillance and protections to discover adverse events promptly and keep their effects minimal. Data and safety monitoring procedures in this study include collection and monitoring of paper-based questionnaires and an organizational structure of clearly defined tasks assigned to all research personnel involved in the conduct of this study. We will keep a thorough record of research activities and completion of scheduled assessments.

- d. For multi-site studies for which the Yale PI serves as the lead investigator:
  - i. How will adverse events and unanticipated problems involving risks to subjects or others be reported, reviewed and managed? *Write here*
  - ii. What provisions are in place for management of interim results? *Write here*
  - iii. What will the multi-site process be for protocol modifications? *Write here*

13. **Statistical Considerations:** Describe the statistical analyses that support the study design.

Statistical procedures and models for analyzing data have been selected according to the research hypotheses being investigated and the types of data available. In general, we will use two-tailed tests and p-values smaller than 0.05 will be considered to indicate statistical significance. When necessary, however, we will use appropriate adjustment of the level of significance (alpha) to account for multiple statistical tests. All statistical analyses will be conducted on an intention-to-treat sample using either SPSS/SAS statistical packages. Baseline characteristics will be analyzed using descriptive statistics.

We will evaluate the efficacy of Invite Only VR at reducing initiation of e-cigarette use (primary outcome). We will test the hypothesis that individuals who play Invite Only VR will be less likely to report the initiation of e-cigarette use in comparison to the control condition. We will conduct a longitudinal analysis using a linear mixed models approach to compare participants in the intervention group to participants in the control group on e-cigarette use from baseline across all follow-up assessments. An advantage of mixed models is that participants with missing data need not be excluded as all available data are used in estimating parameters. We will also use logistic regression models to determine if any relevant baseline variables are associated with rates of initiation of e-cigarette use (constructed as a binary outcome (Yes/No). We plan to evaluate the prognostic significance of a small set of predictor variables (e.g., knowledge, intentions, perceptions, attitudes, social norms, and self efficacy) and use them as covariates in the primary analysis.

